6.1.1 Description of the Test Materials

There are two test materials, a 20% KBR 3023 lotion ('cream') and a 20% KBR 3023 pump spray. Labels are appended.

6.1.2 Trade Name:

KBR 3023 All-Family Insect Repellent Cream KBR 3023 All-Family Insect Repellent Spray

6.1.3 Dosage Form:

Lotion and Pump Spray applied to the skin.

6.1.4 Dose:

Determining dosage is part of the main objective of this study. Dosage for repellency testing will be the mean of the subject means determined for each product in the dosimetry portion of this study. Dosage will be measured in weight and reported by weight and volume.

6.1.5 Manufacturing Site:

Laboratory-prepared by Saltigo GmbH, (Lanxess Group), Germany.

6.1.6 Test Material Storage During Study:

Prior to application, the test materials will be stored indoors, at room temperature and away from direct sunlight or direct sources of moisture or the conditions specified by the sponsor. Storage will be at Carroll-Loye Biological Research.

6.1.7 Test Material Safety:

EPA regulates use of inert ingredients (also termed "other" ingredients) by toxicology profiles in animal tests and by their inclusion in EPA lists of "approved" other ingredients. Ingredients on lists 4a or 4b are considered relatively safe for all uses. The ingredients in the proposed insect repellent formulations are mainly on lists 4a or 4b with a few ingredients on list 3 because of ocular irritation potential. EPA normally regulates the presence of materials on list 3 by labeling to avoid contact with eyes or to prohibit application by children. The other ingredients in the test formulations are commonly used in marketed products for application to human skin as components of cosmetic and drug formulations.

The insect repellent products proposed for testing has been tested in animals for potential oral and dermal toxicity. The active ingredient (KBR 3023) has an extensive toxicity data file, has been previously registered by EPA, and has a positive safety record in consumer use.

A toxicology profile of KBR 3023 is provided in the appendices.

6.1.8 Test Material Composition and Stability:

The test material formulations are typical of topical cosmetics and insect repellent products marketed to consumers. They will be produced under applicable Good Laboratory Practice standards, with records available to EPA. They will be couriered to Carroll-Loye Biological Research, with Chain-of-Custody documented. After that time they will be stored at the Carroll-Loye Offices in a closed cabinet at room temperature (19-24°C). The composition and content of active ingredient in the products used for the proposed efficacy studies will be confirmed by analytical methods prior to and following human subject efficacy testing. The sponsor believes that the formulations will be stable for the duration of the study, based on storage stability studies previously conducted. Additional one-year stability tests are in progress. The EPA has extensive experience with enforcing requirements for such tests based upon their history with similar products applied to humans and LANXESS intends to provide any requested information as appropriate to safety and efficacy issues.

6.2. Negative Control:

6.2.1 Description of the Negative Control

The negative control is untreated for both dosimetry and repellency assays.

6.2.2 Rationale for Employing a Negative Control

Repellent efficacy can only be measured in the presence of biting mosquitoes. In addition, the duration of repellency recorded is likely a function of the number of host-seeking mosquitoes active during the study. The US/EPA uses a standard minimum rate of mosquito attack on untreated subjects to ensure that the repellents under study are sufficiently challenged to provide meaningful data. Traditionally, the measure rate is termed the 'ambient biting pressure'. We adopt that value, but use LIBes ('Lites with Intent to Bite') rather than bites. A mean study LIBe rate of ≥ 1 LIBe per untreated (negative control) lower leg or lower arm per 1 minute is required.

We take several precautions to minimize the probability that untreated control subjects receive any bites (see §§ 5.4, 8.2, 8.3.1, 8.4.1, 10.3.6). Recognizing that individual subjects differ in their inherent attractiveness to mosquitoes, US/EPA science reviewers have recommended that we use two untreated control subjects for this study in order to improve the likelihood of sampling ambient biting pressure in a representative fashion, while still exposing a very small number of untreated subjects to risks from foraging mosquitoes. Having separate untreated subjects also avoids the problem of interaction between treated and untreated limbs that may arise when subjects serve as their own simultaneous controls. In reviewing a similar protocol in May 2006, the California Department of Pesticide Regulation initially requested use of a single negative control, but compromised at two such subjects based on the position of the US/EPA. The prospect of receiving approval to use more than two untreated control subjects is probably small in this case.

There are no controls by which the formulation matrices without the repellent active ingredient are tested. There is no a priori basis for anticipating significant repellent activity in the matrices, and the study objective is to examine efficacy of the end products. The question of whether there is interaction between matrix and active is external to that objective. Accordingly, the added risk of including additional subjects testing matrix-only formulations cannot be justified.

6.3 Comparison Article:

None.

6.4 Test Arthropod Species:

Testing will be conducted with all or some of wild *Aedes vexans*, *Aedes melanimon*, *Aedes taeniorhynchus*, *Culex tarsalis* and *Culex* *pipiens* mosquitoes, and possibly other mosquito species that occur in the same habitats. Mosquito specimens will be collected from untreated control subjects and from the protective clothing of all subjects during testing and identified in the laboratory using taxonomic keys and stereomicroscopy.

7 STUDY SCHEDULE:

7.1	Proposed	Date of	Initiation
7.1	Proposed	Date of	Initiation

To be determine (TBD); within one year of IRB approval.

7.2 Schedule of Events:

Test day	Date	Activities
-30 to -21	ſBD	Begin subject recruitment. Introduce subjects to test plan and procedures; explain compensation; review subject rights and consent forms; option to sign consent forms in order to participate; measure limb surface areas; determine individual dosing behavior and rates, mean dosing rates, and individual dosage values
1 Т	ſBD	Prepare individual dosages for application. Meet with subjects to review day plan and safety procedures. Administer repellent, or do so after travel to field site. Travel to field site. Review safety and data collection procedures. Commence repellency data collection. Monitor subject safety, comfort, comportment, and compliance with data collection protocol.

7.3 **Proposed Date of Completion:**

Experimental Completion Date (Test Day 1): TBD. Final Report Completion Date: TBD.

8 STUDY DESIGN:

8.1 Treatment Groups:

For efficacy testing of each test material, there are two experimental groups, namely 1) a 'treated' group of subjects treated with a single test product, and 2) an untreated ('negative') control group. The dosimetry study is an examination of dosing behavior for each test material. In that study, each subject will be treated, and will also serve as their own untreated control for the dosimeters.

8.2 Experimental Design:

The experiment will be partially randomized by subject. Because the treated condition will be evident to experimenters and subjects, and the test materials are readily distinguishable (opaque lotion versus clear, low viscosity liquid), neither group will be effectively blinded. The clear criteria on which failure is determined (definition of LIBe) will help to eliminate any influence of experimenter or subject bias. Also note that for subject safety, control subjects will be chosen only from among individuals that are experienced in entomological testing or biological science (see §8.3.1, below). Whether arms, legs or both are tested at a given site will depend on the species of mosquitoes present and their behavior. That decision will be made by the Study Director based on reconnaissance of the field sites prior to data collection.

8.3 Randomization Procedures for Repellent Efficacy Testing:

8.3.1 Allocation of subjects to treatment groups:

All subjects that are not untreated controls will be assigned to the treatment group. Treatments will be balanced between arms and legs if both limbs are used. Negative control subjects will be selected exclusively from among experienced personnel. To be regarded as experienced personnel, a candidate subject must have an undergraduate (or higher) degree in life sciences, or be a vector control professional, or have participated in at least five Carroll-Loye repellent efficacy studies. In addition, that person must meet all of the other participation criteria listed in §§9.1.1.1 and 9.1.1.2.

8.3.2 Treatment allocation table:

Materials will be distributed among subjects as tabulated below. Two additional personnel who will monitor ambient biting pressure with untreated limbs during the test are also shown.

Subject	Lotion 1	Pump Spray	Untreated
1	Left limb		
2	Left limb		
3	Left limb		
4	Left limb		
5	Left limb		
6	Right limb		
7	Right limb		
8	Right limb		
9	Right limb		
10	Right limb		
11		Left limb	
12		Left limb	
13		Left limb	
14		Left limb	
15		Left limb	
16		Right limb	
17		Right limb	
18		Right limb	
19		Right limb	
20		Right limb	
21			Left limb
22			Right limb

8.4. Conditional Boundaries or Limits of Study

8.4.1. Ambient 'Lite with intent to bite' Pressure:

A mean study LIBe ('Lite with Intent to Bite') rate of ≥ 1 LIBe per untreated (negative control) lower leg or lower arm per 1 minute is required. No more than 10% '0' values for individual exposure periods are permitted. Ambient LIBe pressure is measured from continuous exposure during 1minute exposure periods commencing once every 15 minutes, beginning at the onset of data collection. Negative control subjects are attended by two assistants who use mechanical aspirators to remove all mosquitoes that LIBe before biting commences.

8.5. Monitoring of Environmental Conditions During the Study

Records will be made of environmental conditions (temperature, relative humidity, wind speed, light intensity and precipitation (presence/absence and general rate/quality) at approximately one-hour intervals throughout the course of the field trial.

9 STUDY PROCEDURES:

9.1 Test Subjects:

9.1.1 Inclusion criteria, all subjects:

9.1.1.1	Age:	18-55 years	
9.1.1.2	Sex:	Male/female	
9.1.1.3	Race:	Any race	
9.1.1.4	Written consent: (see 9.4, below)		
9.1.1.5	Language:	Speak and read English	

9.1.2. Inclusion criteria specific to the two untreated subjects

9.1.2.1 To qualify for candidacy as a subject who exposes untreated skin, an individual must be regarded as competent to do so by the Principal Investigator, must have participated in at least five prior Carroll-Loye repellent efficacy trials, or have participated in at least three such trials and have at least two years of experience as a college life sciences major, or be professionally employed in vector control services.

9.1.3 Exclusion criteria, all subjects:

- 9.1.3.1 Known to be hypersensitive to mosquito bites or exhibiting hypersensitivity during test
- 9.1.3.2 Known to be sensitive or showing sensitivity to any of the test product ingredients, after application.
- 9.1.3.3 Poor physical condition.
- 9.1.3.4 Unwilling to submit to brief query about personal condition.
- 9.1.3.5 Use of insect repellent within one day preceding the study.
- 9.1.3.6 Unwilling to refrain from use of perfumed products, alcoholic beverages or smoking after 9 PM the evening preceding the test and throughout the test.
- 9.1.3.7 Known to be pregnant or lactating. Pregnancy will be self-checked by each female volunteer on the morning of the repellent test using an OTC test kit provided by the Study Director. Results of each such test will be immediately verified by direct inspection by a female technician trained to make that assessment. Only volunteers scored as nonpregnant will be allowed to participate.
- 9.1.3.8 Unable to deliver the test materials to own left and right limbs.
- 9.1.3.9 Unable to see mosquitoes on skin or otherwise effectively monitor and remove mosquitoes that alight on skin.
- 9.1.3.10 Student or employee of the Study Director.
- 9.1.3.11 Does not regularly spend time in outdoor settings.
- 9.1.3.12 Withdraws from testing before receiving a confirming LIBe, when the total exposure duration is less than 90% of the mean of subjects who did not withdraw, and when not more than 2 of 10 subjects have so withdrawn.

If more that 2 of 10 subjects withdraw prematurely, those with the briefest participation will be replaced first. This exclusion factor is not automatically invoked if the Study Director ends exposures due to other factors, such as darkness; in such cases the data collected before termination may be sufficient to meet the study goals.

9.1.4 Number of Subjects and Rationale for Sample Sizes:

In efficacy testing, we will use 10 subjects per treatment and 2 untreated control subjects per field trial. In the dosimetry portion of the study, 10 subjects will be engaged to apply each repellent. Each subject is a replicate.

The number of subjects is chosen as a compromise between several conflicting factors. In the absence of clear means of estimating the distribution of outcome values, it is difficult to predict an ideal sample size. From a strictly scientific standpoint an appropriate response under such circumstances is to increase size, but ethical and economic considerations demand the opposite in the present study, particularly during the efficacy testing phase.

The US/EPA has historically required a minimum of six subjects. Given that test repellents are nearly certain to exhibit greater than zero efficacy, and that testing is conducted under adequate ambient biting pressure, it is nearly certain that no untreated subjects will register fewer or later LIBes than any treated subjects. As a result, from the standpoint of statistical power, six treated and one untreated subject are sufficient to demonstrate a significant treatment effect at P<0.05 (one-tailed test in which all treated values differ in the same direction from the untreated). In the same vein, six is often regarded as a statistically sufficient sample for an observation subset because the increment in the confidence of means estimate begins to drop off sharply at that point. Notably, under the historical guidelines, there seem to have been few problems with EPA registering

repellents that commonly fail to meet their labeled performance specification.

The main scientific risk of using a very small sample is that the probability of over-representing subjects inherently unattractive to mosquitoes is rather large. Note, however, that for US/EPA registration purposes, the test for mosquito repellency is conducted twice, once in each of two ecologically different habitats. In our experience, some or all of the subjects in one test normally do not participate in the other (due to geographic distances between sites). In addition, two negative controls are used for a more robust baseline comparison. Those facts decrease the probability of such sampling error substantially.

However, further considerations indicate that a somewhat larger sample would be superior. Note that the draft EPA guidelines state that the response variable, 'Time to First Confirmed Bite' (or LIBe in this study) is calculated as the average duration for all treated subjects. There is no consideration of variation. In any given study, increasing the number of treated subjects to 10 will improve the probability of estimating the population mean accurately.

The 95% confidence interval computation is useful for assessing the certainty of a means estimate, and for a normal probability density function that interval is ± 1.96 standard error of the mean. In this study we anticipate that the distribution of Times to First Confirmed LIBe will be truncated towards the origin. Because available mean and variance data on efficacy (e.g., Carroll 2006 and other references listed in below) indicate that no individual values will be near zero, approximating the exponential model with the normal model is likely justifiable. Using the rule of thumb that a distribution in which the mean is greater than three standard deviations above zero may be regarded as effectively normal, it is sensible to compute and report the normal 95% confidence interval in this study. Alternatively, if tests indicate substantial deviation from a normal distribution, the deviation will be corrected prior to anlysis.

To consider an example, in a study of repellency employing eight subjects, Cilek et al. (2004) recorded a mean protection time of approximately 180 minutes, with a standard error of about 15 minutes. Had the *N* been six, we can roughly predict that the 95% CI would be 148-212. At N=10, the estimate would be 155-205. At N= 20, the interval would be roughly 162-198. Evidently, adding the additional 10 subjects to reach an N of 20 shrinks the interval, in absolute terms, no more than did the addition of four subjects to increase the sample size from 6 to 10.

To summarize, in the case of a highly efficacious repellent, adding subjects beyond six is likely to increase the precision of the means estimate only slowly. However, the regulatory justification for this study is predicated on an aversion to assuming that efficacy is closely predictable in new formulations. That conservatism is further justified on the basis of the individual and public health importance of avoiding inaccuracy in this study. That position, coupled with the fact that data collection is only 'replicated' once (in a different habitat at that), argues for a prudent approach. To reduce the risk of over-representing atypically attractive subjects, as well the weight of the value obtained from any one subject, we regard 10 (rather than six) treated subjects as a better sample size for the repellency portion of the study.

9.1.5 Individual subject influences on repellent performance and risks from participation, in relation to the choice of subjects

Carroll (2006) reviewed the factors that influence the performance of insect repellents and concluded that there is no *a priori* means of predicting an individual's attractiveness to a particular mosquito population, or likely impact on the data set of a repellency trial. Several studies have indicated that individuals differ in attractiveness to mosquitoes, but that individual attractiveness rankings shift substantially among mosquito taxa. Skin emanated volatiles influence attractiveness, and skin temperature and absorption properties may likewise influence repellent efficacy. The search for general characters to predict repellent performance has led to studies of gender, age, race, hair color, complexion, weight, skin moisture, menses (females), hairiness, and sweat. Of these, only gender has been shown strong and significant effects on individual, in two studies with adequate sample sizes. One of these studies found females to be 25% less attractive to *Aedes* mosquitoes, while that other showed them to be significantly less well protected against *Anopheles* mosquitoes by deet– the opposite pattern. That difference is consistent with further findings that the type of repellent used also interacts complexly with individual subjects and mosquito species in determining efficacy. Nonetheless, because gender effects seem most plausible, we attempt to engage similar numbers of males and females.

For clarity, note that, for example, studies have shown that sweating increases attractiveness to at least one mosquito species. What is not clear is that individuals that sweat more than others, on average, tend to be more attractive to mosquitoes.

On the other hand, it *is* clear that conditions of use strongly influence repellent performance. We intentionally limit our testing to places and times where large number of mosquitoes are active. Further, we expose subject individuals as uniformly as possible to those mosquitoes, and have them engage in behaviors resembling common outdoor activities (walking, sitting, reaching) that may be attractive to mosquitoes. Subjects are monitored to prevent exposure of treated areas to external moisture or abrasion.

Analogous to the summation for repellency, there are few clear patterns permitting us to predict which individuals might be at relatively greater risk from participating in this study. Pregnant and lactating women are excluded on general medical principals, and persons over 55 are excluded due to slightly elevated health risks from West Nile Fever (above), even though the likelihood of contracting the causal agent during a repellent test is very low.

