Field tests are conducted with large populations of arthropods. This permits the analysis of the replicates (data by subject) as independent values. The hypothesis that the test material will significantly reduce the number of mosquitoes LIBing on treated versus untreated skin is not the focus of this study. The focus is to compute, for each test material, a reasonable estimate of mean and standard deviation for the duration between application and repellency breakdown sufficient such that two mosquitoes LIBe on a subject within a half hour period. That pattern is here assessed at a resolution of 15 minutes. The untreated limbs serve to monitor whether the ambient biting pressure remains at or above the EPA standard.

Complete protection time (CPT) is measured as the length of time from initial application to the first confirmed LIBe. A confirmed LIBe is a LIBe followed by another LIBe within 30 minutes. For example, a LIBe at 90 minutes followed by another at 135 minutes is not confirmed, but a third LIBe at 150 minutes would confirm that at 135 minutes, giving a CPT of 135 minutes.

CPT measured in this way will yield a single time value for each subject. Mean CPT will be calculated across all 10 subjects, and will be presented with standard deviation and 95% confidence interval information as well. Ambient LIBing pressure as measured by untreated subjects will be presented tabulated by individual and exposure period. Mean LIBing pressure will be calculated as the number of LIBes received per untreated control subject and per period and span of exposure.

To examine the temporal pattern of failure further, we will employ Kaplan-Meier survival analyses by subject. Kaplan-Meier survival analysis permits us to account for censoring in the event that any subjects withdraw before failure. In addition, we will estimate the Kaplan-Meier median, and the time until 25% failure, for each test product, Variance around median estimates is much more robust than it is around means estimates when censored data are used.

12 STUDY LOCATION(S):

Field sites are in or adjacent to the Central Valley of California or southern California (depending on season). Test site information will be furnished to EPA once it is clear when testing will be permitted, since season influences the availability of test arthropods on both regional and local scales.

13 QUALITY ASSURANCE:

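### Section 9.1.4 defines the reported 95% CI for mean CPT as ±1.96 SE, although the SD comes from only 10 subjects; the multiplier should be t(9) = 2.262

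*Protocol*

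**What the plan says.** Section 9.1.4 of the Protocol sets the sample size: "we will use 10 subjects per treatment and 2 untreated control subjects per field trial". On the confidence interval it states that "for a normal probability density function that interval is ± 1.96 standard error of the mean". It expects the CPT distribution to be truncated towards zero. It argues that a normal approximation is acceptable when the mean lies more than three SDs above zero, and concludes that "it is sensible to compute and report the normal 95% confidence interval in this study". If normality fails, "if tests indicate substantial deviation from a normal distribution, the deviation will be corrected prior to anlysis".

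The section then gives an example. A cited study, described as "in a study of repellency employing eight subjects", had a mean protection time of approximately 180 minutes and a standard error of about 15. For six subjects, "we can roughly predict that the 95% CI would be 148-212". For ten, "At N=10, the estimate would be 155-205". For twenty, the interval is given as roughly 162-198.

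Section 11.3.2, the analysis section, says only that mean CPT "will be presented with standard deviation and 95% confidence interval information as well". It gives no multiplier and no reference distribution.

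**The concern.** The value 1.96 is correct when the standard deviation is known. Here it is not known. Section 9.1.4 itself says there is no clear way to anticipate the distribution of outcomes, and 11.3.2 says the SD will be computed from the study data. With an SD estimated from 10 subjects, the standardised mean follows a t distribution with 9 degrees of freedom, and an interval of ±1.96 SE is too short for its label.

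Neither safeguard in 9.1.4 reaches this. The three-SD rule and the promised correction for non-normality both concern the shape of the distribution. The problem remains when the shape is perfectly normal.

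Mean CPT with its SD and interval is a main reported result, produced for each product at each site for a regulatory submission and for labelling. An interval labelled 95% that covers less overstates how precisely protection time is known.

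**Working it through.** **Inputs.** n = 10 per product and field trial, and multiplier 1.96 (both 9.1.4). Example: mean about 180 min, SE about 15 min at n = 8; printed intervals 148-212, 155-205 and 162-198 for N = 6, 10 and 20 (9.1.4).

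**Step 1: reproduce the printed intervals.** Formula: 180 ± 1.96 × SD/√N.

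- SE exactly 15 at n = 8 gives SD = 15 × √8 = 42.4.
- A single SD of 40 corresponds to SE = 40/√8 = 14.1.

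| N | Printed | z, SD 42.4 | z, SD 40 |
|---|---|---|---|
| 6 | 148-212 | 146.1-213.9 | 148.0-212.0 |
| 10 | 155-205 | 153.7-206.3 | 155.2-204.8 |
| 20 | 162-198 | 161.4-198.6 | 162.5-197.5 |

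With SE taken as exactly 15, the endpoints differ from print by 1.9, 1.3 and 0.6 min. With one SD of about 40, all three agree to rounding. The printed figures are z intervals on approximate inputs, and they reproduce.

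**Step 2: coverage of ±1.96 SE when the SD is estimated.** For normal, uncensored data, coverage = 2 × F(1.96; n-1) - 1, where F is the t distribution function.

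| n | Coverage of ±1.96 SE | t(0.975, n-1) | t / 1.96 |
|---|---|---|---|
| 6 | 89.3% | 2.571 | 1.31 |
| 10 | 91.8% | 2.262 | 1.154 |
| 20 | 93.5% | 2.093 | 1.07 |

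At the planned n = 10 the error rate is 100 - 91.8 = 8.2% instead of 5%. The correct interval is 15.4% wider.

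**Step 3: the example with t.** Formula: 180 ± t(0.975, N-1) × SD/√N. Because the source SE is only approximate, both SDs are shown.

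| N | t, SD 42.4 (width) | t, SD 40 (width) |
|---|---|---|
| 6 | 135.5-224.5 (89.0) | 138.0-222.0 (84.0) |
| 10 | 149.6-210.4 (60.7) | 151.4-208.6 (57.2) |
| 20 | 160.1-199.9 (39.7) | 161.3-198.7 (37.4) |

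**Step 4: the comparison that 9.1.4 draws from the example.** It says that going from 10 to 20 subjects narrows the interval no more than going from 6 to 10.

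- As printed: 64 - 50 = 14 min, then 50 - 36 = 14 min.
- t with SD 42.4: 89.0 - 60.7 = 28.3 min, then 60.7 - 39.7 = 21.0 min.
- t with SD 40: 84.0 - 57.2 = 26.8 min, then 57.2 - 37.4 = 19.8 min.

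The conclusion holds under z and holds more clearly under t.

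**The case against.** The strongest reply is that 1.96 appears only in the sample-size rationale. Section 11.3.2 leaves the multiplier open, so the analyst could compute a t interval without departing from it. In 9.1.4, the word normal closes a discussion of whether a normal model may stand in for an exponential one, which concerns shape. The SD and n will also be reported, so a reader could recompute the interval, and Kaplan-Meier medians and 25% failure times are planned as well.

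Part of this stands. It is not certain that every reported interval will be too narrow. But 9.1.4 speaks of what to compute and report in this study, in the same paragraph that defines the interval as ±1.96 SE, and no other definition is given. That is the natural reading, and leaving 11.3.2 open does not correct it.

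A second reply also stands: 91.8% assumes exactly normal, uncensored data. CPT here is expected to be truncated, is observed on a 15-minute grid and may be censored. The t multiplier removes one known error; it does not guarantee 95% coverage under those conditions.

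A reader might go further and infer that the printed example intervals are arithmetic mistakes. The document does not support that. Its inputs and outputs are given as approximate, one SD of about 40 reproduces all three, and even an SE of exactly 15 leaves every endpoint within 2 minutes. The unrounded source value is not available.

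**Conclusion.** The point holds as a choice of multiplier. As defined in 9.1.4, the interval for mean CPT covers about 91.8% at n = 10 under exact normality without censoring, and it should be about 15% wider, using 2.262 instead of 1.96. The example intervals share this weakness, because they are z intervals for small samples, but they are not miscalculated on their own terms.

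It might also be inferred that the case for 10 subjects is undermined. It is not. The comparison of 6, 10 and 20 becomes more favourable to 10 over 6 under t. The closing paragraph of 9.1.4 rests the choice mainly on limiting the influence of subjects unusual in attractiveness and of any single value. No design decision changes. This is a small correction, worth making because it affects the stated precision of a main result.

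**What to change.** In section 11.3.2, state that any normal-theory 95% confidence interval for mean CPT uses the t distribution with n-1 degrees of freedom (2.262 when n = 10). In section 9.1.4, replace the ±1.96 SE definition with the same rule.

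Recompute the example with t on the same approximate inputs and keep it marked as approximate. With an SE of about 15 at n = 8, the intervals are roughly 135-225, 150-210 and 160-200 for N = 6, 10 and 20.

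The cost is a clause in 11.3.2, an aligned sentence and three replaced intervals in 9.1.4, and reported intervals about 15% wider at n = 10. No additional subjects, procedures or data are needed.
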